### *Statistical Analysis Plan*

*Analyses:* All analyses were carried out in SPSS V29.0.1.1. First, independent sample ttests were used to assess for differences in demographic and clinical variables between those who downloaded their assigned app and enrolled in the trial and those who did not, as well as between the two enrolled groups at baseline, and to compare the baseline scores of treatment completers versus individuals who dropped out of the study and failed to supply follow-up data at post-treatment.

Next, change over time both within group and between groups was examined. Analyses were completed using both per protocol (completer) and intention-to-treat (ITT) (sensitivity analysis) approaches using multiple imputation to estimate missing data. Per protocol analyses only included individuals who completed the post-treatment follow-up questionnaires. ITT (which accounts for that missing data) is generally considered the gold standard in clinical trials, especially longitudinal randomized controlled trial with missing data due to attrition [48], although it has also been criticized for being overly conservative, and for confounding the issues of acceptability and efficacy [49]. We conducted sensitivity analyses using multiple imputation to account for missing data at post-test, the only time point at which between group comparisons were possible. Because the data were missing not at random (MNAR) we used a monotone

imputation with linear regression and 5 iterations. We then analyzed the pooled data using multivariate and univariate analysis of covariance, as well as within group paired sample t-tests.

Initially, paired sample t-tests were used to examine within group change from baseline to immediate post-treatment for each group and to examine maintenance of gains from post CBT treatment to 3- and 6-months follow-up. Subsequently, multivariate and univariate general linear models were used to examine between group effects at post treatment (8 weeks), controlling for baseline levels of the dependent variables.

With respect to between group differences, we first conducted a conservative MANCOVA predicting all outcome measures (dependent variables GSRS, IBSQoL, VSI, GICog, FFQ, BDI) from the independent variable condition, controlling for all of those same measures at baseline. We then ran a series of ANCOVAs predicting each of the outcome measures individually at post-treatment from condition controlling for that measure's baseline value.

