With respect to clinically significant change, we used Jacobsen and Truax's Criterion B (falling within 2 SD of the healthy mean), which is more conservative than Criterion A (falling 2 SD below the pathological mean) [50]. With respect to effect sizes, we report on partial eta squared ( $\eta^2$ ), Cohen's  $d$ , and the pooled pretest standard deviation for weighting the differences of the pre-post-means ( $d_{ppc2}$ ) [51]. The  $d_{ppc2}$  measure is designed for pre-post controlled trials where the sample sizes may be uneven across groups, as was the case in our data set.

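### The plan calls Criterion B stricter than Criterion A without condition, which its own definitions do not support, and its rule for clinically significant change sets no baseline condition

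*SAP*

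**What the plan says.** The last paragraph of the SAP's section Statistical Analysis Plan sets the responder rule: "With respect to clinically significant change, we used Jacobsen and Truax's Criterion B". It defines the rule used and the alternative, and ranks them, in one run: "Criterion B (falling within 2 SD of the healthy mean), which is more conservative than Criterion A (falling 2 SD below the pathological mean"). It attaches no condition to that ranking, and gives no other reason for choosing B.

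The section lists six outcomes ("dependent variables GSRS, IBSQoL, VSI, GICog, FFQ, BDI") and does not say to which of them the rule applies. It gives no healthy or patient mean, SD or numerical cut-off. The rule carries no condition on the baseline score, although the ANCOVAs in the same section do adjust for baseline.

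**The concern.** Two things looked wrong.

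First, each criterion is anchored to a different population. Which one is harder to meet therefore depends on how far apart the populations lie relative to their spreads. An unconditional ranking cannot follow from the definitions. A reader told that the stricter rule was used will take the reported rates as cautious, when they may come from the looser rule.

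Second, the quantity is labelled as change, but the rule describes only a location. If some participants already lie within 2 SD of the healthy mean at baseline, they can be counted as clinically significantly changed without having moved. The absolute responder rates would then mix people who recovered with people who met the rule before treatment.

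**Working it through.** The plan states no figure for this point, so there is none to reproduce. The check is algebra on its two definitions, followed by an illustration on assumed inputs.

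**Step 1: order of the cut-offs.** Take lower scores as better, as the wording of Criterion A implies.

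- Cut-off A = M_patient − 2 SD_patient.
- Cut-off B = M_healthy + 2 SD_healthy.
- B − A = 2(SD_healthy + SD_patient) − (M_patient − M_healthy).

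B is stricter only when B − A is negative, that is, when M_patient − M_healthy > 2(SD_healthy + SD_patient). The two 2-SD ranges must then not overlap. At equality the cut-offs coincide; below it A is stricter. Where higher scores are better, the mirrored algebra gives the same condition. A check on 200,000 random combinations of gap and SDs, in both directions, found no disagreement.

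Break-even gap in patient SDs, 2(1 + r), where r = SD_healthy/SD_patient is assumed:

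- r = 1: 4
- r = 0.5: 3
- r = 0.25: 2.5
- r = 1.5: 5

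**Step 2: how far the two rules can diverge.** Every input here is an assumption and none is in the SAP: normal scores, patient mean 0 and SD 1, healthy mean −G, healthy SD r, post-treatment mean improvement 0.5 SD with unchanged SD. Cut-off A is −2 and cut-off B is c = 2r − G. Break-even is c = −2.

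- Rate under A = Φ(−2 + 0.5) = Φ(−1.5) = 6.7%.
- Rate under B = Φ(c + 0.5).
- Share already inside B at baseline, with no entry limit = Φ(c).
- Rate among those outside at baseline = [Φ(c + 0.5) − Φ₂(c, c + 0.5; ρ)] / [1 − Φ(c)], where Φ₂ is the bivariate normal probability and ρ the baseline to post-treatment correlation.

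| c | Example | Rate A | Rate B as written | Already inside B | Restricted, ρ = 0.7 | Restricted, ρ = 0.5 |
|---|---|---|---|---|---|---|
| 0 | G = 2, r = 1 | 6.7% | 69% | 50% | 48% | 55% |
| −1 | G = 3, r = 1 | 6.7% | 31% | 16% | 22% | 25% |
| −2 | G = 4, r = 1 | 6.7% | 6.7% | 2.3% | 5.5% | 6.0% |
| −3 | G = 5, r = 1 | 6.7% | 0.6% | 0.1% | 0.6% | 0.6% |

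The plan's ranking is right in the last row, a tie in the third and wrong in the first two.

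**Step 3: effect of an entry limit (ρ = 0.7).** With a limit 0.5 SD to the healthy side of cut-off B, the rate as written against the restricted rate is 58% against 48% (c = 0), 27% against 22% (c = −1) and 6.3% against 5.5% (c = −2). With a limit at or beyond cut-off B on the patient side nobody starts inside, and the two rates are equal.

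**Step 4: a group contrast in rates (0.5 SD improvement against none, ρ = 0.7, no entry limit).** As written, the contrast is Φ(c + 0.5) − Φ(c).

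| c | As written | Restricted | Difference |
|---|---|---|---|
| 0 | 0.6915 − 0.5000 = 19.1 points | 22.7 points | +3.6 |
| −1 | 0.3085 − 0.1587 = 15.0 points | 13.4 points | −1.6 |
| −2 | 0.0668 − 0.0228 = 4.4 points | 3.9 points | −0.5 |

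The shift is small and does not keep one sign. The SAP describes no test of such a contrast, so this shows scale only.

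**The case against.** On the ranking, the fair reply is that the SAP is written in the past tense about measures already analysed. The clause may describe the norms the authors had in hand rather than state a general rule. If those populations are far enough apart, it is correct. Deleting it would change no cut-off, count or test. All of that stands. What remains is that the document states the ranking without condition, rests its choice of B on it, and supplies nothing from which it could be verified.

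On the baseline condition, the plan speaks of change and of falling within a range, and the ordinary sense of those words may be movement into it. Entry criteria normally sit in the protocol, which is not at hand, and a suitable limit would remove the problem for the measure it governs. This stands too, and it makes the effect conditional. It does not close the matter. The text admits two readings that can give different counts, and an entry limit on one measure need not protect the others among the six.

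Restricting the denominator is also not the only convention. Showing the share in the healthy range alongside the baseline share would be informative as well. The baseline comparisons that the SAP plans, between groups and between completers and dropouts, bear on whether the groups started alike. They do not show how many participants started inside the range.

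A reader might infer that B was in fact the looser rule in this trial, or that the reported rates are inflated. The document supports neither inference, because it gives no norms, cut-offs or entry limits.

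**Conclusion.** The point holds in a limited form. As a general statement the ranking of B over A is false: it needs a mean gap above 2(SD_healthy + SD_patient), and below that gap the order reverses. This part is algebra and rests on no assumption beyond the plan's definitions. Whether the ranking fails for any measure here cannot be determined.

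The missing baseline condition is less certain, because it depends on a literal reading and on the absence of an entry limit at or beyond the cut-off. Its size rests wholly on assumed inputs. In the no-limit cases shown at correlation 0.7, the as-written rate exceeds the restricted one by about 21 percentage points at c = 0 (69% against 48%), by 1.2 at c = −2 (6.7% against 5.5%), and by practically nothing at c = −3.

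Severity is minor. Only the descriptive responder rates and their interpretation are touched. It would be wrong to conclude that the trial's main comparisons are in doubt: the MANCOVA and ANCOVA do not use this rule.

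**What to change.** Three changes to the paragraph on clinically significant change:

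- Remove the claim that B is the more conservative criterion, or support it measure by measure by stating the healthy and patient means and SDs used and the two resulting cut-offs.
- Count clinically significant change only among participants who were outside the healthy range at baseline and are inside it at post-treatment.
- Report, by group, the number already inside the range at baseline for each measure to which the rule is applied.

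The cost is a wording change and a recount from baseline and post-treatment scores already held. The downside is a smaller denominator and possibly lower reported rates.

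### The only directional between-group effect size the SAP defines, d_ppc2, is a change-score contrast without regression adjustment for baseline, so it does not estimate the effect as the ANCOVA does, and no adjusted difference in scale points is named

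*SAP*

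**What the plan says.** In the Analyses part of the SAP, the between-group comparison is a general linear model of "between group effects at post treatment (8 weeks), controlling for baseline levels of the dependent variables". It is run first as a MANCOVA of all six outcomes, "controlling for all of those same measures at baseline", and then as one ANCOVA per outcome, "predicting each of the outcome measures individually at post-treatment from condition controlling for that measure's baseline value".

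The closing paragraph of the SAP names three effect sizes. It opens the list with "With respect to effect sizes, we report on partial eta squared", adds Cohen's d, and ends with d_ppc2, described as the "pooled pretest standard deviation for weighting the differences of the pre-post-means". It says that this last measure "measure is designed for pre-post controlled trials where the sample sizes may be uneven across groups" and adds that group sizes were in fact uneven in this data set.

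The SAP mentions no baseline-adjusted mean difference and no confidence interval. It does not say whether Cohen's d is a within-group or a between-group quantity, or which means and SD enter it.

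**The concern.** The test and the directional effect size are different contrasts. The ANCOVA removes from the post-treatment difference only the part of the baseline difference that carries forward through the regression slope. d_ppc2 removes all of it. When the arms differ at baseline the two give different answers, so a reader may see a d_ppc2 that is larger or smaller than the effect to which the ANCOVA p-value belongs.

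The other measures do not fill the gap. Partial eta squared belongs to the ANCOVA, but it does not show which arm did better or by how many points on the GSRS or IBSQoL. Cohen's d cannot be interpreted until it is defined. Readers comparing or pooling app trials would therefore take d_ppc2 as the between-group effect, although the same ANCOVA yields a more precise estimate.

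**Working it through.** The SAP gives no effect size, group size, SD, pre-post correlation or baseline imbalance, so there is no figure to reproduce. The form of the test and of d_ppc2 comes from the SAP. Every number below is an assumption for illustration.

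**Gap in a single trial.** Let Y be the difference between arms in post-treatment means, X the difference in baseline means, and b the fitted pre-post slope.

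- Change-score contrast (numerator of d_ppc2): Y − X
- ANCOVA effect: Y − bX
- Difference: (Y − X) − (Y − bX) = −(1 − b)X, of size (1 − b) × |X|

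Dividing by the pooled baseline SD puts this in SD units:

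| Imbalance | b = 0.4 | b = 0.6 | b = 0.8 |
|---|---|---|---|
| 0.2 SD | 0.12 | 0.08 | 0.04 |
| 0.3 SD | 0.18 | 0.12 | 0.06 |

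The SD of a chance baseline imbalance is √(2/n) per arm: √(2/50) = 0.20 and √(2/30) = 0.26. A 0.2 SD imbalance is thus an ordinary result with 50 per arm, while 0.3 SD is 1.5 SDs out.

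**Precision.** With equal pre and post SDs and correlation ρ (so that b = ρ), in units of the variance σ²:

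- Change score: (2/n) × 2(1 − ρ)
- ANCOVA: (2/n) × (1 − ρ²)
- Ratio of variances: 2/(1 + ρ); ratio of interval widths: √(2/(1 + ρ))

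For ρ = 0.4, 0.6 and 0.8 the width ratio is 1.195, 1.118 and 1.054, that is, about 20%, 12% and 5% wider.

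Cross-check with 50 per arm and ρ = 0.6: the ANCOVA variance is 0.04 × 0.64 = 0.0256 (SE 0.16) and the change-score variance is 0.04 × 0.80 = 0.0320 (SE 0.179). The excess, 0.0064, is 0.08², the square of the typical gap (0.4 × 0.20 = 0.08).

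**Simulation.** There were 3,000 trials per scenario, with group sizes 30/50 and 60/60, correlations 0.3, 0.5 and 0.7, and a true effect of 0 or 0.5 SD.

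- The mean gap between d_ppc2 and the standardised ANCOVA effect was at most 0.007 in size.
- The per-trial SD of the gap was 0.07 to 0.16 (30/50) and 0.06 to 0.13 (60/60).
- With a true effect of 0.5 SD, a t-test on change scores and the ANCOVA fell on different sides of two-sided p = 0.05 in 11% to 24% of trials (30/50) and 4% to 22% (60/60). The signs differed in at most 3%. The SAP plans no between-arm change-score test, so this only shows how far the two contrasts can diverge.

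**Partial eta squared.** For the 1-df condition term, F = η² × df / (1 − η²), with df the error degrees of freedom. η² therefore fixes F and p exactly; the p-value was recovered from it in every simulated trial.

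**The case against.** The strongest reply is that the SAP already reports an effect size tied to its test. Partial eta squared for the condition term determines F and p, so it cannot disagree with the ANCOVA. That stands. A reader might infer that the SAP's effect sizes in general can contradict its p-values; this is possible only for d_ppc2, and for Cohen's d depending on how it is defined.

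Second, a reader might infer that d_ppc2 was preferred to an ANCOVA effect because of uneven group sizes, or is the headline result. The text supports neither. It describes what the measure is designed for, reports it beside the ANCOVA, and ranks none of the three measures. It remains true that uneven group sizes do not in themselves call for a change-score contrast, since ANCOVA accommodates them.

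Third, a reader might take Cohen's d to be unadjusted for baseline. The SAP does not say, so the defect is a missing definition.

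Fourth, the SAP does address clinical meaning, through a criterion for clinically significant change. That is fair, but the criterion classifies individual patients and gives no between-group difference in points.

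Finally, no test or p-value is at fault, and nothing in the SAP forbids reporting adjusted means. This is a matter of reporting, and it limits the weight of the point. It does not remove it, because the SAP names a directional between-group measure and that measure is not the effect tested.

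**Conclusion.** The point holds as a mismatch between test and effect measure, and as a loss of precision. The discrepancy is (1 − slope) × imbalance: 0.08 SD for a 0.2 SD imbalance at slope 0.6, which is half the ANCOVA standard error of 0.16 SD with 50 per arm. The interval for the change-score contrast would be 5% to 20% wider over correlations of 0.8 to 0.4. Slopes, correlations, arm sizes, imbalances and equal pre and post SDs are all assumed. The discrepancy vanishes as the slope nears 1 or the imbalance nears 0.

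A reader might go further and infer that d_ppc2 is systematically biased towards the arm that started worse. The SAP does not support this. Under randomisation both contrasts have the same expectation, so the gap is chance; it favours one arm only given an observed imbalance, and the SAP shows none. One caution applies: the per-protocol analysis keeps only people with post-treatment questionnaires, so imbalance among those analysed need not be pure chance. Neither contrast is then protected, and the SAP gives no basis for a direction or size of bias.

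This is an inexpensive improvement to reporting. It does not undermine the planned tests.

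**What to change.** In the effect-size paragraph at the end of the SAP:

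- Make the main between-group effect for each outcome the adjusted mean difference in scale points, with its 95% CI, from the univariate ANCOVA. Name that model, because the MANCOVA adjusts for a different set of covariates.
- Give the same difference divided by the pooled baseline SD, and state for each scale which direction is benefit.
- Keep d_ppc2 as a supplementary value for comparison with other studies, labelled as not ANCOVA-adjusted. Keep partial eta squared alongside.
- Define Cohen's d: within or between groups, and which means and SD.

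The ANCOVAs are already run, so the cost is SAP wording and one more results column. An adjusted difference with its standard error also pools directly across the imputed data sets. The downside is that the reported effect may turn out smaller than d_ppc2.
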